6.10 PEGFILGRASTIM (NEULASTA)

Source and Pharmacology:

Pegfilgrastim is the pegylated form of recombinant methionyl human G-CSF (filgrastim). Pegfilgrastim is produced by covalently binding a 20-kilodalton (kD) monomethoxypolyethylene glycol molecule to the N-terminal methionyl residue of filgrastim. The molecular weight of pegfilgrastim is 39 kD. G-CSF is a lineage specific colony-stimulating factor which regulates the production of neutrophils within the bone marrow and affects neutrophil progenitor proliferation, differentiation, and selected end-cell functional activation (including enhanced phagocytic ability, priming of the cellular metabolism associated with respiratory burst, antibody dependent killing, and the increased expression of some functions associated with cell surface antigens). After subcutaneous injection the elimination half-life of pegfilgrastim ranges from 15 to 80 hours and the time to peak concentration ranges from 24 to 72 hours. Serum levels are sustained in most patients during the neutropenic period postchemotherapy, and begin to decline after the start of neutrophil recovery, consistent with neutrophil-dependent elimination. After subcutaneous administration at 100 mcg/kg in 37 pediatric patients with sarcoma, the terminal elimination half-life was 30.1 (+/- 38.2) hours in patients 0 to 5 years-old, 20.2 (+/- 11.3) hours in patients 6 to 11 years-old, and 21.2 (+/- 16) hours in children 12 to 21 years-old.

Pegfilgrastim Toxicity:

Likely (happens to 21-100 children out every 100 children)	Less Likely (happens to 5-20 children out every 100 children)	Rare (happens to < 5 children out every 100 children)

 • Mild to moderate medullary bone pain 	
 • Local pain or irritation at injection site • Headache • Increased alkaline phosphatase, lactate dehydrogenase and uric acid. • Thrombocytopenia 	
 • Low grade fever • Allergic reactions (anaphylaxis, angioedema, or urticaria) • Generalized erythema and flushing • Splenomegaly • Splenic rupture • Sickle cell crises in patients with sickle cell disease (SCD) • Excessive leukocytosis • Sweet's syndrome (acute febrile neutrophilic dermatosis) • Adult respiratory distress syndrome

Unknown frequency and timing: Fetal toxicities and teratogenic effects of pegfilgrastim in humans are unknown. Conflicting data exist in animal studies. It is unknown whether the drug is excreted in breast milk.

Supplier: Commercially available. See package insert for further information.

Formulation and Stability:

Supplied as a preservative-free solution containing 6 mg (0.6 mL) of pegfilgrastim (10 mg/mL) in a single-dose syringe with 27 g, ½ inch needle with an UltraSafe® Needle Guard. The needle cover of the prefilled syringe contains drug natural rubber (a derivative of latex). Store refrigerated at 2°-8°C (36°-46°F) and in the carton to protect from light. Prior to injection, pegfilgrastim may be allowed to reach room temperature protected from light for a maximum of 48 hours. Avoid freezing.

Guidelines for Administration: See Treatment and Dose Modifications sections of the protocol

6.11 LOPERAMIDE

Formulation and Stability: Supplied as a clear, cherry flavored syrup (1 mg/5 mL) or as a scored green caplet (2 mg).

Mechanism of Action: Loperamide HCl acts by slowing intestinal motility and by affecting water and electrolyte movement through the bowel

Toxicities: Overdoses of loperamide HCl may result in CNS depression, constipation, and nausea. Children may be more sensitive to CNS effects than adults.

Supplier: Commercially available. See package insert for further information.

6.12 Drug Inventory Records

The investigator, or a responsible party designated by the investigator, must maintain a careful record of the inventory and disposition of all drugs.

7.0 REQUIRED OBSERVATIONS/MATERIAL AND DATA TO BE ACCESSIONED

7.1 Clinical and Laboratory Studies

Blood and urine studies must be performed within 2 weeks of study enrollment. Tumor disease evaluation (including appropriate imaging studies, bilateral bone marrow aspirate and biopsy for standard histology and urine catecholamines) are required within 3 weeks of study entry and subsequent to any prior therapy. Echocardiogram and ECG are required within 4 weeks of study entry and subsequent to any prior therapy. Initiation of protocol therapy is required within 1 week of study enrollment.

References to second course of therapy in the following table are only relevant to patients enrolling prior to Amendment 7A.

OBTAIN OTHER STUDIES AS NEEDED FOR GOOD PATIENT CARE.

Observation	Before Entry	Days -1 to +7 of Each Course ¹	Days 8 to 43 of each Course	Day 43 to 50 of each Course
Physical Exam ⁵ (Ht, Wt, BSA, VS) Performance status only at entry	X	Day 4 (+/- 1 day)	Every other week	X
CBC, Diff, Platelets ⁵	X	Day 4 (+/- 1 day)	Twice weekly ²	X
AST, ALT ⁵ , Total ⁵ + Direct Bilirubin, Albumin	X	Day 4 (+/- 1 day)	Weekly	X
BUN, Serum Creatinine ⁵	X	Day 1 prior to MIBG infusion for Vorinostat Arm Only and Day 4 (+/- 1 day) for All Patients	Weekly	X
PT/INR and PTT ⁵	X	Weekly on Vorinostat Arm	Weekly on Vorinostat Arm	X
Electrolytes, Calcium, Magnesium, Phosphorus	X	Day 4 (+/- 1 day)	Weekly	X
T ₄ , TSH	X			X
Serum β-HCG ^{3,5}	X			X
MUGA or Echocardiogram ⁵	X			X
Electrocardiogram ⁵	X	Vorinostat Arm Only: Day 4 (+/- 2 days)		X (Vorinostat Arm Only)
Urinalysis	X			X
Urine catecholamines VMA/HVA	X			X
Bilateral BM Aspirate + Biopsy for morphology ^{4, 7}	X			X
Blood and Marrow for N04-05	X			X
Anatomic imaging (CT or MRI scan) of chest/abdomen/pelvis plus any other known sites of measurable disease ⁴	X			X
MIBG diagnostic scan (REQUIRED) ^{4, 5} Use same isotope with each scan	X			X
MIBG whole body scan		On release from radiation isolation		
Whole body dosimetry		Days 1 to 4 ⁶		
Blood for biology studies (if consent)		See Section 8	See Section 8	
Archival slides for biology studies (if consent)		See Section 8		

1. No other routine bloodwork/radiology studies are required while patient is hospitalized unless clinically indicated. Patients with prior electrolyte imbalance should be monitored during the hydration.
2. Continue until ANC $> = 500$ cells/ μ L and platelet count $> = 20,000$ cells/ μ L x 3 days without transfusion then weekly until Day +43.
3. Obtain for females 10 years of age and older or post-pubertal.
4. Tumor imaging = CT and/or MRI (Chest abdomen pelvis) plus CT/MRI imaging of any other sites with MIBG update, MIBG for optimum visualization of all areas of bulk tumor (primary & metastasis) as well as chest/abdomen/pelvis. CT or MRI of chest/abdomen/pelvis + any other known lesions of tumor (repeat of chest/abdomen/pelvis CT or MRI is required even if scans are negative for tumor at study entry). If patient has a history of tumor lesions in the skull, orbits or brain, OR if MIBG scan shows uptake in these same areas, then a CT or MRI of the brain/orbits is strongly suggested. For patients with epidural or hepatic tumor lesions, MRI is the recommended imaging technique. All disease status tests must be performed ≤ 3 weeks prior to study entry and subsequent to any intervening therapy
5. Required for verification of eligibility. All results should be faxed to NANT Operations Center with study registration eligibility. An eligibility worksheet is available in the data forms packet on NANT website (www.nant.org).
6. See section 4.3.7 for dosimetry guidelines.
7. Bilateral bone marrow aspirates and biopsies to be performed at each disease evaluation, even if negative at study entry.

7.2 Recommended Follow-Up Observations

The following are recommendations only, but may be altered at discretion of treating physician. Repeat the following if abnormal on a monthly basis until stable or normalized after the end of therapy. If normal at the end of therapy then repeat only as clinically indicated:

- History, physical exam (Ht, Wt, VS)
- CBC/Differential, Platelets, AST, ALT, Bilirubin, BUN, Creatinine
- T₄, TSH and MIBG scan every 3 months until 1 year post treatment, then every 6 months for 3 years or until progression, death or other therapy.

Patients will be followed for life for any delayed toxicities related to protocol therapy and for the development of second malignancies.

Data on patients who undergo subsequent myeloablative therapy within 6 months of completing protocol therapy will be collected to assess the incidence and severity of SOS in these patients (Aim 1.10).

After completion of protocol therapy, the disease status, sites of relapse, and last alive date will be recorded until first relapse/progression or until patient receives another non-protocol therapy, after which only last alive date will be reported, as well as date of death and cause of death (if applicable). In addition, those patients who undergo subsequent myeloablative therapy within 6 months of completing protocol therapy will be followed for the development of SOS within 21 days following the infusion of stem cells post-myeloablative treatment.

7.3 Documentation of Tumor Response

Patients will undergo complete disease re-staging between Day 43 and Day 50 of each course of therapy (only a single course of therapy allowed for patients enrolling with Amendment 7A and later). It is recommended that all scans and tests previously done to document tumor lesions be performed in subsequent evaluations of disease status.

All patients will have diagnostic bone marrows performed with each disease evaluation, regardless of involvement at study entry. To confirm a bone marrow response of CR, an additional bone marrow examination for morphology (for a total of 2 bone marrow exams) must be done a minimum of three weeks apart (section 11.2.1).

Once a patient receives therapy other than prescribed on this protocol, no further scans or bone marrow evaluations will be required for this protocol since the patient will no longer be evaluable for response to protocol therapy.

8.0 CORRELATIVE BIOLOGY STUDIES

Collection of samples for correlative biology studies is optional and not required for study entry. Although these studies cannot be mandated, all institutions are strongly urged to submit specimens for all consenting patients.

Aside from submission of archival tissue to quantify NET expression (section 8.3), these studies are to be performed during both courses of therapy for patients enrolling prior to Amendment 7A and during the single allowed course of therapy for patients enrolling with Amendment 7A and later.

8.1 Evaluation of Minimal Residual Disease by 5 Gene NB5 assay TaqMan low density array (TLDA) Assay

All patients are required to co-enroll onto the NANT Biology Study, N04-05. Patients should submit blood and/or bone marrow at study entry and at the time of day 43-50 restaging studies. Submission of blood and bone marrow for NB5 TLDA assay will be according to the instructions in N04-05. Patients can submit only bone marrow for NB5 TLDA assay if blood volumes for research do not allow for blood submission.

8.2 Evaluation of Blood Markers of Radiation Exposure

8.2.1 Sample requirements

The following samples will be obtained at each time point (see section 8.2.2):

- 2.5 mL of peripheral blood in PAXgene RNA blood tube (provided by the study)
- 5 mL of peripheral blood in EDTA (usually purple top) tube
- 5 mL of peripheral blood in serum separator (usually red top) tube

8.2.2 Sampling scheduling

Samples will be obtained according to the following schedule. **Note that the schedule differs slightly based upon randomized arm of the study to which a specific patient has been assigned.**

Sample Timepoint (Obtain in Each Course)	Samples to be Obtained
Baseline Draw #1 
 For ¹³¹I-MIBG only arm: Anytime on the day prior to ¹³¹I-MIBG infusion (Protocol Day 0) For ¹³¹I-MIBG/vorinostat arm: Prior to first dose of vorinostat (Protocol Day -1) For ¹³¹I-MIBG/irinotecan/vincristine arm: Prior to first dose of vincristine/irinotecan (Protocol Day 0) 	2.5 mL in PAXgene RNA blood tube 5 mL in EDTA (usually purple top) 5 mL in serum separator (usually red top) tube
Baseline Draw # 2 Day of ¹³¹ I-MIBG infusion, anytime prior to start of infusion (all patients) = Protocol Day 1	2.5 mL in PAXgene RNA blood tube 5 mL in EDTA (usually purple top) 5 mL in serum separator (usually red top) tube
72 hours (+/- 2 hours) from start of ¹³¹ I-MIBG infusion (all patients) = Protocol Day 4	2.5 mL in PAXgene RNA blood tube 5 mL in EDTA (usually purple top) 5 mL in serum separator (usually red top) tube
96 hours (+/- 2 hours) from start of ¹³¹ I-MIBG infusion if patient still admitted to hospital (all patients) = Protocol Day 5	2.5 mL in PAXgene RNA blood tube 5 mL in EDTA (usually purple top) 5 mL in serum separator (usually red top) tube
Protocol Day 15 (or whenever patient receives stem cell infusion, if stem cell infusion does not occur on Day 15)	2.5 mL in PAXgene RNA blood tube 5 mL in EDTA (usually purple top) 5 mL in serum separator (usually red top) tube

8.2.3 Sample processing

- PAXgene tubes:** After collecting blood into a PAXgene tube, the tube should be gently inverted 8-10 times. Keep the tube at room temperature for 2 - 72 hours and then freeze upright in a wire rack (not Styrofoam holder) for 24 hours at -20°C and then transfer to -70 or -80°C freezer until batch shipment.
- EDTA tubes:** Blood from EDTA tubes will be used to obtain fixed cells for γ -H2AX testing (using the SmartTube system) and plasma for flt3 ligand testing. Once collected, EDTA tubes should be gently inverted 6-8 times and transferred to the treating center's specimen processing lab immediately. Upon arrival in the specimen processing lab, remove 1 mL of whole blood, place the 1 mL of whole blood into a SmartTube (provided by the study), cap tightly, and for process as described below. Reserve the remaining 4 mL of whole blood for plasma isolation as described below.
 - SmartTube Processing:** Once 1 mL of whole blood has been added to the SmartTube, activate the tube manually. To activate a SmartTube manually,

make sure the cap is screwed on securely and then bend the SmartTube in the middle until you feel the ampoule inside break, then invert the SmartTube 10 times to ensure good mixing. Incubate the activated SmartTubes at room temperature for 8 minutes.

After the 8 minute incubation, immediately transfer the SmartTubes to a -80°C freezer or place in direct contact with dry ice. The SmartTubes should be stored at -80°C until ready for batch shipment. Samples frozen in SmartTubes should not be stored at temperatures warmer than -80°C. Smart Tubes have not been validated for storage in liquid nitrogen. Retain frozen until ready for batch shipment.

- **Plasma Isolation:** Centrifuge the samples in a refrigerated centrifuge (4°C) for 10 minutes at 1500 g or greater. Next, remove the plasma using a transfer pipette and transfer the plasma into at least two cryovials with a minimum of 0.5 mL plasma per cryovial. Cap the vials securely and label as described below. Immediately freeze the plasma in an upright position in a -70°C to -80°C freezer. Retain frozen until ready for batch shipment.
- **Serum separator tubes:** Allow the blood to clot at 4°C (or in a bucket with ice) for at least 30 minutes but no longer than 2 hours. Centrifuge the blood at 1000g for 15 minutes at 4°C (preferred) or room temperature to separate the serum (top, straw-colored layer) from the red blood cells (bottom, red layer). Aliquot the serum into at least two cryovials with a minimum of 0.5 mL serum per cryovial. Cap the vials securely and label as described below. Immediately freeze the serum in an upright position in a -70°C to -80°C freezer. Retain frozen until ready for batch shipment.

8.2.4 Sample labeling

PAXgene tubes, SmartTubes, plasma aliquot tubes, and serum aliquot tubes should be labeled with the patient's NANT ID number, the protocol number N11-01, the date of blood draw, "Course 1" or "Course 2", and one of the following indicators of the sample timing:

--Baseline draw 1

--Baseline draw 2

--Hour 72

--Hour 96

--Day 15 (label as "Day 15" even if drawn on a different day due to timing of stem cell infusion)

No other identifiers should be included on the label.

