This amendment adds a late blood draw (protocol Day 15 at time of stem cell infusion) to extend the correlative radiobiology studies. Since it is possible that the markers under investigation as part of Aim 1.6 remain elevated at the 72 and 96 hour time point, it is of interest to determine whether these markers return to baseline by Day 15 and whether failure to return to baseline by Day 15 correlates with increased risk of toxicity. Changes were made to Sections 10.1 and 10.3.1. Section 10.1 clarifies how protocol enrollment will be handled during performance of scheduled interim analyses and a change to Section 10.3.1 clarifies the definition of evaluable for response in a secondary per-protocol analysis. Clarifying language has been added to Section 6.3 to accommodate local needs at one MIBG treating center. Additional updates include changes in the site investigator at Stanford, change in protocol coordinator, updated address for shipment of correlative radiobiology samples, and minor editorial changes.

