4.4 Autologous Peripheral Stem Cell Infusion for All Treatment Arms

4.4.1 Stem Cell Timing/Dosage

Peripheral blood stem cells will be infused on Day 15 of each course for all patients. In situations in which the DMSO concentration in the stem cell product would exceed an accepted level for infusion within a 24 hour period, stem cell products may be infused over two days to meet this standard.

Stem cell infusion may occur sooner if indicated (i.e. due to an infectious or bleeding complication) after consultation with the Study Chair, Study Vice Chair, or designee.

Stem cell infusion is planned for 2 weeks after ^{131}I -MIBG infusion (Day 15). However, stem cells may be infused in the window +/- 2 days from planned date to avoid weekend or holiday stem cell infusions. If the ^{131}I -MIBG infusion is delayed due to production or logistical reasons, the date of stem cell reinfusion should be re-dated for 14 days after ^{131}I -MIBG infusion.

The minimum dose for peripheral blood stem cells is 1.5×10^6 viable CD34+ cells/kg. Patients planning to receive a stem cell dose of $1.5 - 1.9 \times 10^6$ CD34+/kg must have a back-up aliquot of $1.5 - 1.9 \times 10^6$ CD34+/kg available until a minimum of 6 patients have been rescued with stem cell dose of $1.5 - 1.9 \times 10^6$ CD34+/kg without delayed engraftment (section 4.7). If the first 6 patients receiving this reduced stem cell dose do not have delayed engraftment, then future patients may enroll with only a minimum of 1.5×10^6 CD34+ cells/kg and no back-up aliquot. If any of the first 6 patients have delayed engraftment, then the required stem cell dose will be changed to 2.0×10^6 CD34+ cells/kg and sites alerted to this change via consortium memo.

Patients planning to receive a stem cells dose of $\geq 2.0 \times 10^6$ CD34+/kg are not required to have a back-up aliquot at any time during the study.

For patients whose body weight exceeds ideal body weight (IBW) by more than 20%, adjusted body weight may be used for calculation of PBSC dose (Reference: [Bone Marrow Transplant](#). 40(7):665-9; Appendix VI).

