10.7.2 Minimal Residual Disease by NB5 Assay

We will use TLDA to determine the ability of each the three ^{131}I -MIBG regimens to reduce peripheral blood and bone marrow disease burden. Peripheral blood and bone marrow samples will be obtained at study entry and at the time of subsequent bone marrow evaluations. For each patient, we will calculate

their change in TLDA DG score from baseline to end of course 1 of therapy. The primary analysis will be an analysis of variance to compare this change in TLDA DG score in the bone marrow between randomized treatment groups. Secondary analyses will include evaluations of change in peripheral blood TLDA DG score as well as baseline level of blood and bone marrow disease burden by TLDA as predictors of response to ¹³¹I-MIBG therapy.

10.7.3 Evaluation of γ -H2AX Foci, Flt3 Ligand, Amylase, and DNA Damage Response Genes

For each radiation biomarker of interest, we will focus on comparing changes in each biomarker across the three randomized treatment arms. Each biomarker is a continuous variable, with values measured at 5 time points (two pre-¹³¹I-MIBG and one each at hours 72, 96, and Day 15 after start of ¹³¹I-MIBG infusion). We will determine the relative (percent) change of the post-¹³¹I-MIBG values from 2nd evaluation for each biomarker for each patient. The changes from the 1st to the 2nd value in the ¹³¹I-MIBG only arm will be used to estimate the within patient variability, while changes from the 1st to 2nd value in the other two arms will reflect the impact of each radiation sensitizer alone on each marker. Changes post ¹³¹I-MIBG will be presented in context with the estimated inpatient variation.

To determine the effect of radiation sensitizers on each biomarker, we will use an analysis of variance (comparing treatment arms) with repeated measures (change at 72 hours, at 96 hours, and at Day 15) to model the relative change of each biomarker as a function of randomized treatment arm and time. We will introduce a linear contrast to assess the general impact of the presence or absence of a radiation sensitizer (combining the irinotecan and vorinostat arms). Additional models will evaluate calculated whole body radiation exposure as a covariate in the model and separately as the outcome variable as a function of randomized treatment arm.

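### Section 10.7.3 analyses the blood sample taken on the stem cell day as a nominal Day 15 value and ignores the actual draw date, which can bias its association with toxicity

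*Combined protocol and SAP*

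**What the plan says.** - **Draw rule.** Section 8.2.2 schedules the fifth sample for "Protocol Day 15 (or whenever patient receives stem cell infusion, if stem cell infusion does not occur on Day 15". The row has no time window and does not require the blood to be taken before the cells go in. By contrast, the 72- and 96-hour rows have windows of 2 hours either way, and the second baseline draw must precede the 131I-MIBG infusion.
- **What moves the infusion.** Section 4.4.1 gives three routes. For complications: "Stem cell infusion may occur sooner if indicated (i.e. due to an infectious or bleeding complication", after consultation with the study leadership and with no earliest day stated. For logistics: "stem cells may be infused in the window +/- 2 days from planned date to avoid weekend or holiday stem cell infusions". For a late 131I-MIBG dose, "the date of stem cell reinfusion should be re-dated for 14 days after" the actual infusion, so a production delay does not change the time since radiation.
- **Label.** Section 8.2.4 keeps the Day 15 name "even if drawn on a different day due to timing of stem cell infusion", but the same label must also carry "the date of blood draw".
- **Purpose.** The Amendment 6 rationale in Section 2.7 says the draw was added partly to learn "whether failure to return to baseline by Day 15 correlates with increased risk of toxicity".
- **Analysis.** Section 10.7.3 models "repeated measures (change at 72 hours, at 96 hours, and at Day 15" by arm. It then uses two-sample t-tests of baseline values and changes against response, and against grade 3 or higher non-hematologic toxicity and grade 4 or higher neutropenia or thrombocytopenia in that course. It counts 24 tests per outcome (6 biomarkers, 4 times), with nominal p-values. The opening of Section 10.7 calls the correlative studies descriptive.

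**The concern.** The event that can bring the draw forward is the same kind of event that defines the outcome. Section 2.2 reports that most grade 3 and 4 non-hematologic toxicities in the earlier phase II study were febrile neutropenia and other infections. A patient infused early for such a complication is sampled closer to the radiation dose. If the marker is still falling, the value is high for a true Day 15 and reads as failure to return to baseline. The toxicity came first, yet the analysis would show a slow-recovering marker alongside toxicity, which is the pattern the sample was added to look for.

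The arm comparison is exposed in the same way if early infusions are more common in one arm. Section 4.8.1.2 foresees neutropenia with serious infection on Days 6 to 12 in the vorinostat arm, so such events before Day 15 are within the plan's expectations.

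A smaller matter is that a tube drawn after the infusion starts may contain infused cells that were never exposed to this 131I-MIBG course. That would matter for the cell-based assays (gamma-H2AX and gene expression) more than for plasma Flt3 ligand or serum amylase.

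**Working it through.** **1. The plan's own figures (Section 10.7.3).** Participation: 0.80 x 105 = 84 patients, 84 / 3 = 28 per arm. Tests: 6 x 4 = 24 per outcome. Power for a one-way comparison of 3 arms at 0.05, with largest and smallest means one sigma apart and the third midway: noncentrality = 28 x (0.5² + 0² + 0.5²) = 14 on 2 and 81 degrees of freedom, giving 91.8% against the stated 91%. These figures reproduce, and none depends on when the Day 15 blood is drawn. Day 15 is one of the four times, so 6 of 24 tests per outcome are affected.

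**2. Is the draw day handled anywhere?** Sections 8.2.2, 8.2.4 and 10.7.3 contain no analysis window for this sample, no adjustment for actual draw day, and no rule separating toxicity that began before the draw from toxicity that began after it.

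**3. Size of the artefact.** With no true association, the expected difference between toxicity groups, in SD units, is

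shift = (share of toxicity patients drawn early) x (days early) x (marker slope per day).

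Examples: 0.05 x 5 x 0.2 = 0.05 SD; 0.20 x 5 x 0.2 = 0.20 SD.

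**4. Effect on the planned t-test.** Inputs:
- 84 patients (Section 10.7.3).
- Toxicity in 31%, from 22% grade 3 plus 9% grade 4 in Section 2.2, assuming no patient is counted in both.
- Assumed, because the documents are silent: the share drawn early, 3 to 7 days early, and slopes of 0.1 to 0.3 SD per day. All other draws are spread evenly over Days 13 to 17.

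The marker is unrelated to toxicity except through draw day. Rejection rates of the nominal 5% test, 3,000 simulated trials per cell:

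| Toxicity patients drawn early | 3 days, 0.1 SD/day | 5 days, 0.1 | 5 days, 0.2 | 7 days, 0.3 |
|---|---|---|---|---|
| 0% | 0.045 | 0.045 | 0.047 | 0.050 |
| 5% | 0.045 | 0.050 | 0.056 | 0.074 |
| 10% | 0.053 | 0.059 | 0.062 | 0.128 |
| 20% | 0.051 | 0.068 | 0.126 | 0.329 |
| 50% | 0.086 | 0.179 | 0.499 | 0.927 |

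The test is two-sided, so under this null a rising marker with the same slope gives the same rates in the opposite direction.

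**5. With the recorded date.** Adding actual draw day as a covariate gave rejection rates of 0.040 to 0.061 across all these cells. The simulated trend is linear in day, so the adjustment model is correct by construction; a curved trend would be corrected less completely.

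**6. Arm comparison.** If one arm had 10 percentage points more early draws than another (assumed), the shift would be 0.10 x 5 x 0.2 = 0.10 SD, or 0.10 x 7 x 0.3 = 0.21 SD at the steepest setting. The comparison is powered for 1 SD.

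**The case against.** The strongest reply is that this is a minor issue in an exploratory analysis. Aim 1.6 is exploratory, samples are optional, the studies are called descriptive, and resampling is planned as a robustness check. The default draw is Day 15, the ordinary movement of 2 days either way is for weekends and holidays, and an earlier infusion is an exception that needs consultation. All of this stands and limits the weight of the point. It does not remove it: nominal p-values will still be reported, and resampling the same mistimed values does not correct their timing.

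A reader might infer more than the documents support, in three ways:

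- *Toxicity sets the draw time and so creates the association.* This is true only of infusions moved for a complication. How often that happens is not stated, and at 5% the distortion is slight.
- *Early draws always look like failure to recover.* Section 2.6.5 has amylase already falling by hour 96 but Flt3 ligand still rising in some patients; Section 2.6.3 has gamma-H2AX decreasing by hour 120. A marker back at baseline before the early draw gives no bias, and a rising one gives bias the other way. Residual radioactivity is therefore not a safe stand-in for marker level.
- *The true timing is lost.* It is not. The draw date is on every tube, so the gap lies in the analysis text.

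**Conclusion.** The point holds as a gap in Section 10.7.3. The plan uses a nominal time for a sample whose real time can depend on the outcome, and the result can be a created, inflated or masked association. The size cannot be fixed from the documents. Under the stated assumptions it runs from nothing visible, if few toxicity patients are infused early or the marker is flat, to rejection in most trials, if half are drawn a week early on a steep slope. Nothing in the documents shows that the upper end is likely.

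The reach is limited to the Day 15 tests and the Day 15 term of the repeated-measures model. The 72- and 96-hour results and the primary response endpoint are untouched. The change is still worth making: it is cheap, and the tests at risk are the ones Amendment 6 added this sample to support.

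**What to change.** In Section 10.7.3:
- Compute days from the start of 131I-MIBG to the draw, using the date on the label. Use this in place of nominal Day 15, as a covariate in the Day 15 toxicity and response tests and as the time value in the repeated-measures model.
- Add a sensitivity analysis limited to draws on Days 13 to 17, which is 12 to 16 days after an infusion on Day 1. Keep early-infused patients in the main analysis. Dropping them there would replace toxicity-dependent timing with toxicity-dependent missing data.
- For the toxicity association, count only toxicity with onset after the draw, or report toxicity before and after the draw separately.

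In Section 8.2.2, state that this sample is taken before the stem cell infusion starts. Stem cell timing stays as it is.

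The cost is a few sentences of protocol text and a little more analysis. The analysis changes also work for samples already collected, provided toxicity onset dates are on the case report forms, which the documents do not show. One limitation remains and should be stated: adjusting for date does not remove any direct effect of an active infection on a marker.
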